+ extended family: a family that extends beyond the nuclear family, including grandparents, aunts, uncles, and other relatives, who all live nearby or in one household.

Patient recruitment and management

The households will be classified into nuclear family type and extended family type. The "Nuclear family type" is defined as husband and wife with baby (aged less than 5 months) and with or without children (2-5) and the "Extended family type" (three-generation family) is defined as husband and wife with baby (aged less than 5 months), children (2-5), and grandparents aged > 65 years old. The exclusion criteria are co-morbid medical conditions of the baby such as chronic lung disease, cyanotic congenital heart disease, neuromuscular disease and a primary immunodeficiency. We will initially complete an enrollment form to collect baseline data, including patient demographics, prior medical history, season when discharge, neonatal course and households. A LINE-based management will be done weekly by study team to see if there are any respiratory symptoms in household. In addition to the monthly physician weekly LINE response, the research nurse will contact the parents or legal guardians by telephone monthly for the 24 months to obtain data on changes in baseline information, and specific facts regarding possible respiratory infections after the last contact.

Study endpoint

The primary endpoint is the *S. pneumoniae* and RSV isolation rates in children and their household contacts of different family type. The secondary endpoint is the serotype of *S. pneumoniae* and RSV in post-PCV13 era.

Study design

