If the households present with **respiratory symptoms**, the visit will be arranged as early as possible. When they presenting to the emergency department, outpatient clinic, or inpatient ward, the urine will be collected for the serotype-specific urinary antigen detection (SSUAD) assays in adult households and the nasopharyngeal or throat swab for PCR will be performed to study serotype of *S. pneumoniae* and RSV subgroup. If the subjects who have clinical syndromes suggestive of pneumonia or bronchopneumonia, they will be asked to participate in the further study along with their household family members. Nasopharyngeal aspiration, urine, blood, and induced sputum will be collected for cultures, PCR and serological test. Clinical manifestations, disease course, and outcomes will be recorded. Family members in the same household will be asked to undergo screening with a nasopharyngeal or throat swab and urine sample. We will trace back 2-week contact history of children in nuclear family who get RSV or pneumococcal infections, especially focus on other family members. The data will be further analyzed to evaluate the influence of short period and long period contact.

Case report form will be used to collect information about the family members, including demographic data, the number of bedrooms in the house, amount of contact time with the patient, presence and pattern of current or recent signs and symptoms and contact history with persons outside of the household who had clinical syndromes suggestive of *S. pneumoniae* or RSV infection.

Follow-up telephone interviews repeated questions about signs and symptoms at 2, 4, and 8 weeks. If any household family member reported experiencing signs or symptoms suggesting *S. pneumoniae* or RSV infection during the follow-up period, clinical assessment and laboratory investigation will be repeated.

	Data collection	Specimen collection
Enrollment	1. information consent form 2. baseline data, including patient demographics, prior medical history, season when discharge, neonatal course and households	
Line follow up period	Checking if there are any respiratory symptoms	
Index case presents symptoms suggesting upper respiratory tract infection		Index case 1. Serotype-specific urinary antigen detection (SSUAD) assays 2. Nasopharyngeal or throat swab for PCR will be performed to study serotype of S. pneumoniae and RSV subgroup. RSV will be sequenced to ascertain F protein heterogeneity.

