Index case presents symptoms suggesting lowerer respiratory tract infection	Index case 1. Clinical manifestations, disease course, and outcomes will be record. Family members 1. Questionnaire-based interviews will be used to collect information bedrooms in the house, amount of contact time with the patient, presence and pattern of current or recent signs and symptoms and contact history with persons outside the household who had clinical synfromes suggestive of S. pneumoniae or RSV infection.	Index case 1. Routine clinical examination of nasopharyngeal aspiration, urine, blood and induced sputum will be collected for culturws, PCR and serological tests. Family members 1. Family members in the same household will ased to undergo screening with a nasopharyngeal or throat swab and urine sample.
Post first episode	Follow-up interviews repeated questions about signs and symptoms at 2, 4, and 8 weeks. If any household family member reported experiencing signs or symptoms suggesting S. pneumoniae or RSV infection during the follow-up period, clinical assessment and laboratory investigation will be repeated.	

LINE management

Establish a LINE group with the parent or guardian. The family will response back weekly or when they have acute respiratory infection (ARI) symptoms/signs. We will contact them monthly to fill out a Google Questionnaire.

Serotype-specific urinary antigen detection (SSUAD) assays

Urine specimens of adult households will be collected and stored at -80°C for SSUAD assays.

RSV PCR for RSVA and RSVB

Direct molecular detection of RSV Types A & B from nasopharyngeal swabs will be done by using HiberGene's RSV A/B Combo. The F protein gene will be amplified by RT-PCR using primers described in our previous study [32]. RSV genotypes will be assigned after alignment with reference sequences and subsequent phylogenetic analysis using MEGA software (Version MEGA 7.0.26). For this purpose, the best-fit nucleotide substitution model will be calculated. Phylogenetic trees will be constructed using the maximum likelihood algorithm and the General time-reversible model with a gamma distribution of 5. To test the tree stability bootstrap values of 1,000 will be used.

Antimicrobial Nonsusceptibility Testing

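### Contacts are swabbed for two different reasons that the plan never separates, so a crude contact isolation rate can differ by family type with no true difference

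*Combined protocol and SAP*

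**What the plan says.** **Route 1, own symptoms.** The Study design text provides that when a household member presents with respiratory symptoms, "the nasopharyngeal or throat swab for PCR will be performed to study serotype of" the pneumococcus and the RSV subgroup. After a first episode, members are interviewed at 2, 4 and 8 weeks, and if anyone reports suggestive symptoms, "clinical assessment and laboratory investigation will be repeated".

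**Route 2, household screening.** Subjects with "clinical syndromes suggestive of pneumonia or bronchopneumonia, they will be asked to participate in the further study along with their household family members" set off a wider investigation: "Family members in the same household will be asked to undergo screening with a nasopharyngeal or throat swab and urine sample". No symptom condition is attached to those family members.

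The schedule table agrees with the text. The row headed "Index case presents symptoms suggesting upper respiratory tract infection" lists specimens for the index case only. Family swabs and urine appear only in the row headed "Index case presents symptoms suggesting lowerer respiratory tract infection". No swab is listed at enrolment, and none is scheduled for contacts who are well in a household without lower respiratory illness.

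**Endpoint and analysis.** Study endpoint defines the primary endpoint as the pneumococcal and "RSV isolation rates in children and their household contacts of different family type". It gives no denominator and does not mention reason for swab. Statistical Methods offers chi-square or Fisher's exact tests for categorical variables, and a three-level mixed model (HGLMEM). The model's clinical covariates are named only in general terms. Neither swab trigger nor symptom status at swab is listed.

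**The concern.** A swab taken because the contact is ill and a swab taken because someone else is ill answer different questions, and there is no reason to expect the same positivity from both. The contact rate in each family type is a weighted average of the two, with weights set by how often each route operates.

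Those weights can depend on family type. By definition the extended household adds grandparents and includes children aged 2-5, whom the nuclear household may lack. Each additional member is another person whose lower respiratory illness would bring every other member in for screening. The share of screening swabs can therefore be higher in extended households even when each person's risk of illness is the same. Any difference between family types in the frequency of lower respiratory illness would add to this or offset it.

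At stake is the comparison that the primary endpoint is built on. A crude difference in contact isolation rates could reflect why people were swabbed and not how often they acquire the organism. A real difference could be masked in the same way.

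**Working it through.** **1. The plan's own figure, for scale.** Power/Sample Size gives 80% power, 5% significance, 29-46% in nuclear and 38-50% in extended families, and 93 per group. With 29% v 50%, two-sided, the usual two-proportion formula gives 83.9 per group. With continuity correction it gives 93.2, which matches 93 (94 if rounded up). Of the pairs of range ends and midpoints tried, only this one comes close. The difference that reproduces the plan's number is thus 21 points. Like ends of the ranges differ by 9 points (29% v 38%) and 4 points (46% v 50%).

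**2. Can the mix differ with equal individual risk?** Assumptions, not in the documents: each contact has one own-symptom swab, and each other member has a lower respiratory episode with probability q between 0.1 and 0.3, after which the contact is screened. In a household of m members:

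symptomatic share = 1 / (1 + q(m − 1))

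| q | nuclear, m = 3 | nuclear, m = 4 | extended, m = 6 |
|---|---|---|---|
| 0.1 | 1/1.2 = 83% | 1/1.3 = 77% | 1/1.5 = 67% |
| 0.3 | 1/1.6 = 63% | 1/1.9 = 53% | 1/2.5 = 40% |

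Household size alone moves the mix.

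**3. Effect on the crude rate when there is no true family-type difference.** Let w be the symptomatic share, and let p_s and p_a be detection in symptomatic and screening swabs, equal in both family types.

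crude rate = w·p_s + (1 − w)·p_a, so false difference = (w_N − w_E)(p_s − p_a)

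The detection rates are borrowed from the ends of the planning ranges. The plan does not give them as rates by reason for swab.

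| p_s, p_a | 70% v 50% | 80% v 40% | 90% v 30% |
|---|---|---|---|
| 50%, 38% | 0.20 × 12 = 2.4 | 0.40 × 12 = 4.8 | 0.60 × 12 = 7.2 |
| 46%, 29% | 0.20 × 17 = 3.4 | 0.40 × 17 = 6.8 | 0.60 × 17 = 10.2 |
| 50%, 29% | 0.20 × 21 = 4.2 | 0.40 × 21 = 8.4 | 0.60 × 21 = 12.6 |

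(Columns are symptomatic share, nuclear v extended; entries are percentage points.)

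With the shares from step 2 for 3 v 6 members, the same formula gives from (0.833 − 0.667) × 12 = 2.0 to (0.625 − 0.400) × 21 = 4.7 points. For 4 v 6 members it gives from (0.769 − 0.667) × 12 = 1.2 to (0.526 − 0.400) × 21 = 2.7 points. Household size alone therefore supports the lower part of the range. The upper part needs family types to differ in more than the number of members.

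**4. Chance of a false positive.** For a pooled two-proportion test with 93 independent swabs per group (an assumption, since the plan gives no swab count), the chance of p < 0.05 with no true difference rises from 5% to 6-9% at 70% v 50% and to 17-41% at 90% v 30%.

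**The case against.** **The plan does not say that it pools.** This stands. A reader might infer from the endpoint that ill and well contacts will be combined in one rate. The documents do not state that; they leave the denominator undefined. The point is therefore conditional: nothing in the plan prevents a crude rate, and the chi-square or Fisher comparison as written would be one.

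**Asymptomatic contacts are the only ones affected.** A reader might also infer that contacts go unswabbed unless the index case has lower respiratory illness. That is not so. Contacts with symptoms are swabbed on their own account, and it is this that creates the mixture.

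**The needed data are partly planned.** Also true. The case report form records family members' current and recent symptoms, and the HGLMEM has room for clinical covariates. But the plan does not name reason for swab or symptom status at swab, and the unadjusted tests have no place for them.

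**Separating by reason is not a complete cure.** This stands too. The screening group contains both ill and well contacts, so reason for swab alone leaves a mix within it. Symptoms may also result from infection, so conditioning on them changes what is estimated.

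**Strata cost precision.** They do, and the loss can be substantial. If 93 swabs per family type split 70/30 and 40/60, the within-route comparisons are 65 v 37 and 28 v 56. For 29% v 50%, power falls from 84% to about 56% and 45%. A single adjusted estimate should lose less.

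**The sampling scheme is unsettled.** Statistical Methods refers to weekly household visits, sampling intervals and a baseline infection status, none of which has a matching swab in the schedule. This does not answer the concern. It is a further reason to state who is swabbed, when and why.

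**Conclusion.** The concern holds as a gap in the analysis plan. Two routes lead to a contact swab, the endpoint and analyses do not distinguish them, and a crude contact isolation rate by family type can differ when true rates are equal.

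Its size and direction cannot be worked out from the documents. Under the assumed detection rates and swab mixes the artefact is about 2 to 13 points. It is about 1 to 5 points if household size is the only thing that differs. That is below the 21-point difference that reproduces the sample size, but comparable with the 4 and 9 points separating like ends of the planning ranges.

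A reader might take a figure in double digits as the expected bias. The documents do not support that: it arises only with both a wide gap in detection and a very unequal mix. The direction depends on which route gives higher positivity and which family type has more screening. The plan should deal with this before analysis, because a choice made once results are seen would be data-driven.

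**What to change.** 1. Code two items for every contact swab: reason for swab (own symptoms, including repeats after follow-up interviews, or household screening after a suspected lower respiratory case) and symptom status at the time of the swab.
2. Include both as fixed effects in the HGLMEM, and name the adjusted family-type comparison as the main contact result.
3. Report contact isolation rates by family type within each category, with the denominator stated. Do not rest the conclusion on the crude pooled rate.
4. State that these results describe positivity given the reason for swab, not unconditional carriage.
5. Reconcile the weekly visits, sampling intervals and baseline infection status in Statistical Methods with the Study design text and schedule table.

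The cost is one or two coded fields and some added wording, with no extra swabs. Precision falls, more for the category-specific rates than for the adjusted estimate.

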Households with at least 1 ARI case during the study period will be included for data analysis. A household with ARI in different years will be treated as 2 different households. Because household visits will be conducted weekly, we will collect specimens for ARI episodes as possible. We will identify these ARI through symptom records. The ARI cases in RSV or *S. pneumoniae* whose dates of onset are within 10 days before or after RSV or *S. pneumoniae* onset will be identified and defined as preceding and subsequent ARI, respectively. We will apply a Bayesian approach to estimate acquisition and clearance rates for RSV or *S. pneumoniae* in a susceptible-infected-susceptible model [37]. The inference relies on repeated measurements of the current status of being a non-carrier (susceptible) or a carrier (infected) of one of the pathogens. We will collect the measurements with sampling intervals. The index cases are the first members of the household to have clinically apparent illness confirmed by laboratory studies. The secondary cases are defined as other family members whose respiratory symptoms occurred later than the index cases' illness. Identified source of infection within the household is defined as the first case in the household who displayed clinically apparent disease and who have clear contact history with individuals outside the household who had illnesses suggestive of *S. pneumoniae* or RSV infection. The infection transmission interval will be defined as the time between the onset of disease for the first case in the household and the onset of disease in a secondary case [38].

Hierarchical generalized linear mixed effect models (HGLMEM)

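### The 2-week contact trace-back is written for nuclear families and for no other group, so source and contact-duration findings would not be comparable by family type

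*Combined protocol and SAP*

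**What the plan says.** All references are to the combined protocol and SAP.

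- **Trace-back (Study design).** "We will trace back 2-week contact history of children in nuclear family who get RSV or pneumococcal infections". The sentence ends by putting the emphasis on contact with the rest of the family. The next sentence gives its use: "The data will be further analyzed to evaluate the influence of short period and long period contact".
- **Groups (Patient recruitment and management).** "The households will be classified into nuclear family type and extended family type". The nuclear type is a couple with a baby, with or without older children. Only the extended type includes grandparents over 65.
- **Where the groups are compared.** The primary endpoint (Study endpoint) is "isolation rates in children and their household contacts of different family type". The sample size is framed on household-acquired pneumococcal infection in each family type. The mixed model has a household group by time term.
- **Source definition (Statistical Methods, Infected model).** An identified household source is the first clinically ill case, among those "who have clear contact history with individuals outside the household" who were themselves ill.
- **Other contact data (Study design).** The case report form asks family members about contact time with the patient and about "contact history with persons outside of the household who had clinical syndromes suggestive of" either infection. It has no family-type limit and no stated 2-week window.
- **Aim (Significance).** Household transmission is to be established with emphasis on the elderly and on infants and children.

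**The concern.** The trace-back sentence names one of the two comparison groups. The procedures around it (swabs and urine from household members, the case report form, and the interviews at 2, 4 and 8 weeks) name neither. A site following the text would take a structured 2-week history for an infected child in a nuclear household and would have no instruction to do so in an extended one.

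Whether a contact history is clear enough to meet the source definition depends on how it was sought. If the search differs by family type, then who is named as the source, which way transmission is judged to have run, and how long the contact lasted can all differ by family type for reasons unrelated to transmission. Grandparents live only in the extended type, so the trace-back would add nothing on the elderly. A 2-week recall history also cannot be reliably recovered once the episode has passed.

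**Working it through.** The plan gives no figure for the trace-back, so there is none to reproduce. The point is settled by comparing the text.

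**1. What each family type receives, as written**

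| Procedure | Nuclear | Extended |
|---|---|---|
| Swab and urine screening of household members | yes | yes |
| Case report form: contact time, outside contacts | yes | yes |
| Interviews at 2, 4 and 8 weeks (signs and symptoms) | yes | yes |
| 2-week contact trace-back of infected children | yes | not stated |

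**2. Does the case report form close the gap?** In part. It covers contact time and outside contacts in both types, but it differs from the trace-back in two ways.
- It states no 2-week window.
- The schedule table puts these questions in the lower-respiratory row. As the table reads, the upper-respiratory row has no data-collection entry. The trace-back is triggered by any RSV or pneumococcal infection in the child. On that reading, an upper-respiratory RSV episode could prompt a contact history in a nuclear household and none in an extended one.

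**3. Which results depend on it?** The primary isolation rates and the secondary serotype endpoint rest on specimens collected without a family-type limit, so this sentence does not bias them directly. Source attribution, direction of transmission and short- against long-contact results depend on contact history, so they are exposed.

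**4. How large could the effect be?** This is illustration only: every detection rate below is assumed. The planned 120 households per group less 15% loss gives 120 × 0.85 = 102 per group. Using 102 as a number of episodes assumes one qualifying episode per retained household. The test is a two-proportion test at two-sided 5%.

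*(a) Trace-back finds more outside sources.* Assume 60% of episodes in both groups truly have one, and the form alone finds 50% of them.
- Trace-back finds 80%: 0.60 × 0.80 = 48% against 0.60 × 0.50 = 30%, a false gap of 18 points. Pooled proportion 0.39; null SE √(0.39 × 0.61 × 2/102) = 0.0683; alternative SE √((0.48 × 0.52 + 0.30 × 0.70)/102) = 0.0671. The chance of p < 0.05 is Φ((0.18 − 1.96 × 0.0683)/0.0671) = Φ(0.69), about 75%.
- Trace-back finds 60%: 36% against 30%, a gap of 6 points, and a chance of about 15%.

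*(b) Trace-back finds more household sources.* Assume 44% of infections in both groups are truly household-acquired (the midpoint of the plan's 38–50% for extended families), with 90% correctly attributed when traced. Nuclear families then show 0.44 × 0.90 = 39.6%.

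| Attributed without trace-back | Extended observed | False gap | Chance of significance in that direction |
|---|---|---|---|
| 80% | 35.2% | 4.4 points | about 10% |
| 70% | 30.8% | 8.8 points | about 26% |
| 60% | 26.4% | 13.2 points | about 52% |

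Under (a), nuclear families look more often infected from outside. Under (b), they look more often infected at home. The direction therefore depends on which contacts the trace-back reveals, and the documents do not settle that.

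*(c) Number of episodes.* If only 29–50% of the 102 households qualified (the outer limits of the planning rates, a rough proxy), n would be 102 × 0.29 ≈ 30 to 102 × 0.50 = 51. The 75% in (a) would fall to about 30–46%. RSV and repeat episodes would push n back up.

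**The case against.** The strongest reply has four parts.

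- **The text does not say only.** The restriction is inferred from naming one group and from silence on the other. The note under the figure in Study site and population defines a nuclear family generically as a couple and their dependent children, and the extended family as reaching beyond it. The phrase could therefore mean the children of the core unit in any household. This stands as a reason to ask for clarification. It does not remove the problem, because the term is also a defined study group and the Power/Sample Size section uses it that way.
- **The trace-back looks mainly inward.** Its stated focus is on other family members, whereas the source definition turns on contact outside the household, which the case report form covers in both types. This stands. It weakens any claim that the trace-back would mainly raise outside-source detection, and it is one reason the direction is uncertain.
- **No between-type comparison of sources or contact duration is written.** The contact-duration analysis could be meant for nuclear families alone. This also stands. If so, the plan should say so, since family type is the comparison that runs through the rest of the study.
- **Size.** A reader might infer that the primary comparison is biased, or that an 18-point artefact should be expected. The documents support neither: the specimens behind the isolation rates are collected in the same way in both types, and the 18 points come from assumed detection rates and an assumed 102 episodes per group.

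**Conclusion.** The point holds in a limited form. As written, the 2-week trace-back is assigned to one of the two family types, and the form used in both only partly makes up for this. Source attribution, direction of transmission and contact-duration results would not be comparable by family type, and the trace-back would leave out the households with grandparents. The primary isolation rates are not directly biased. The size and direction of any bias are unknown. The assumed values above give false gaps of about 4 to 18 points, which shows only that the effect could be small or material. The conclusion rests on reading nuclear family as the defined study group, which is the more natural reading but not a certain one. It would be wrong to infer that extended families give no contact history at all. The change is worth making because it is cheap now and the missing histories could not be reliably recovered later.

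**What to change.** In Study design, replace the trace-back sentence with one stating that a 2-week contact history will be traced for every child with RSV or pneumococcal infection, in both nuclear and extended families, with the same form, questions and trigger. Add it to the schedule table.

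If the restriction is intended, give the reason, confine source and contact-duration analyses that use trace-back data to nuclear families, and state that they will not be compared by family type.

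The cost is a few more interview questions in extended families, asked at contacts already planned (weekly LINE checks, monthly calls and episode visits). The sample size does not change.

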Strategies to prevent these interactions to reduce the incidence of *S. pneumoniae* and RSV infection are very important in children as well as the elderly. The elderly might colonize with *S. pneumoniae* first and then get the RSV acquisition from the younger households. Vaccine delivery should be justified by detailed understanding of *S. pneumoniae* and RSV transmission dynamics. The determinants include carriage rate, age distribution, infection severity, and presence of concurrent *S. pneumoniae* or RSV in the same household. This household-based prospective cohort study aims to establish the household transmission of RSV and *S. pneumoniae* especially in the elderly and infants/children as well as inter-relationship between *S. pneumoniae* and RSV. We hope our data can be utilized in the AI fields to develop a model to predict the transmissions in the exceedingly early stage of disease of *S. pneumoniae* and RSV and strategy of prevention.

Preliminary Data

Our previous data suggest that interactions between RSV and *S. pneumoniae*. RSV infections can increase the ability of adherence of *S. pneumoniae* 15 A in Hep2 cell.

We selected 13 patients for the RSV genotype and 16S ribosomal RNA test. The 16SrRNA revealed *S. pneumoniae* was the predominant bacterial in the nasopharyngeal site.

[figure not shown]
RSV	RSV genotype	16SrRNA
A	ON1	Streptococcus pneumoniae
B	BA9	Streptococcus pneumoniae
A	ON1	Streptococcus pneumoniae
B	BA9	Haemophilus influenzae
A	ON1	Streptococcus salivarius
B	BA9	Streptococcus thermophilus
A	ON1	Streptococcus pneumoniae
B	BA9	Streptococcus lactarius
B	BA9	Streptococcus pneumoniae
A	ON1	Streptococcus pneumoniae
B	BA9	Streptococcus pneumoniae
B	BA9	Propionibacterium acnes
B	BA9	Streptococcus pneumoniae

Study site and population

A **household-based prospective cohort** study will be conducted from 2021 to 2025 in northern Taiwan. We will invite 240 households, having a baby who is discharged from MacKay children's Hospital.

Around 20 babies per months for 12 months adding up to 240 babies in total. The estimation is based on historical discharge number from NBR MacKay Memorial Hospital Taipei. The number is also proved feasible in previous studies.

[figure not shown]
* nuclear family: a couple and their dependent children, regarded as a basic social unit.

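### Routine symptom surveillance names only the parent or guardian as contact and asks about the household as a whole, so grandparents' milder illnesses, found in one comparison group only, may be captured less completely

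*Combined protocol and SAP*

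**What the plan says.** **Who is contacted.** Under LINE management: "Establish a LINE group with the parent or guardian". The next sentence reads "The family will response back weekly or when they have acute respiratory infection (ARI) symptoms/signs", without saying who answers for whom. Patient recruitment and management adds that "the research nurse will contact the parents or legal guardians by telephone monthly for the 24 months". A monthly Google questionnaire is also mentioned, but its items are not reproduced.

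**What is asked.** Patient recruitment and management: "A LINE-based management will be done weekly by study team to see if there are any respiratory symptoms in household". The unit of the question is the household.

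**Where grandparents appear.** The extended type is defined with "children (2-5), and grandparents aged > 65 years old"; the nuclear type has none. The footnote on extended families under Study site and population describes relatives "who all live nearby or in one household".

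**What a report sets off.** Under Study design, when respiratory symptoms occur "the visit will be arranged as early as possible", and specimens are taken. In the schedule table, an upper respiratory illness leads to specimens from the index case only. A lower respiratory illness also leads to a swab and urine sample from family members in the same household, with no requirement that they have symptoms. Interviews at 2, 4 and 8 weeks after a first episode lead to repeat work-up if any family member reports symptoms.

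**How the data are used.** The primary endpoint is isolation rates in children and household contacts by family type. The Infected model section identifies acute respiratory infections (ARIs) from symptom records, analyses only households with at least one, and separates index from secondary cases by the order of illness. It also says household visits are weekly, which the procedural sections do not describe.

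**The concern.** A parent knows of their own illness and the baby's directly, but may hear of a grandparent's cold late or not at all, especially if the grandparent lives nearby and not in the same home. If so, detection is weaker for a role that exists in only one of the two groups compared.

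Three results are exposed:

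- **The comparison by family type.** Ascertainment may differ between groups, and no planned analysis can recover episodes that were never recorded. A household whose only ARI was an unreported grandparent illness leaves the analysis set altogether.
- **Case order.** If a grandparent fell ill first and this went unreported, a later case becomes the index. If the grandparent was second, a secondary case and its transmission interval are lost. The Significance section states an interest in transmission "especially in the elderly and infants/children", so these are the chains of most interest.
- **The longitudinal model.** The hierarchical model treats infection status within individuals. A household-level reply does not show which members were asked about and were well.

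**Working it through.** **1. Tracing each route by which a grandparent can be tested**

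| Route | Needs a report of the grandparent's own symptoms? | Respondent stated? |
|---|---|---|
| Weekly LINE check | Yes | Group set up with parent or guardian; the family replies |
| Monthly call | Yes | Parents or legal guardians |
| Interviews at 2, 4 and 8 weeks | Yes | Acts on any member's report; respondent not named; only after a first episode |
| Screening after another member's lower respiratory illness | No | Not applicable; limited to the same household |
| Weekly household visits (Infected model only) | Unclear | Not described in the procedures |

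A grandparent's mild illness, when no one in the home has a lower respiratory illness, is therefore sampled only if reported. The routine channels for that report name the parent or guardian.

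**2. The plan's own figure**

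Power/Sample Size gives 93 per group at 80% power and 5% significance, for 29-46% (nuclear) against 38-50% (extended). For 29% vs 50%, two-sided, mean 0.395, difference d = 0.21:

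n₀ = [1.96√(2×0.395×0.605) + 0.8416√(0.29×0.71 + 0.50×0.50)]² / 0.21² = (1.355 + 0.568)² / 0.0441 ≈ 83.9

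With continuity correction: n = (n₀/4)[1 + √(1 + 4/(n₀d))]² = 20.97 × 2.108² ≈ 93.2, which rounds up to 94.

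So 93 is close to what the widest contrast in the stated ranges needs. This serves below only as a yardstick; the concern does not rest on it.

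**3. Illustration of size (assumed inputs)**

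The documents give no capture rates. Assume 90% capture when reported first-hand and 50-80% by proxy. The relative shortfall for grandparents is

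- 1 − 0.80/0.90 = 11%
- 1 − 0.50/0.90 = 44%

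Multiply by an assumed grandparent share of extended-family contact episodes:

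- share 40%: 0.40 × 11% = 4%; 0.40 × 44% = 18%
- share 20%: 0.20 × 11% = 2%; 0.20 × 44% = 9%

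**4. Illustration on the planning rates (assumed inputs)**

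Observed extended rate = true rate × (1 − share × fraction missed), with share 20-40% and fraction missed 10-50%:

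- mildest: 0.50 × (1 − 0.20×0.10) = 0.49
- strongest: 0.50 × (1 − 0.40×0.50) = 0.40

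Against 29%, the difference falls from 21 points to between 20 and 11. Power at 93 per group (two-sided, uncorrected) falls from 84% to between 80% and 35%. Against 46%, the difference moves from +4 points to between +3 and −6.

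**5. Direction**

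Steps 3 and 4 hold only if the rate is infections per person followed. Study endpoint gives no denominator. If the rate is positives per episode tested, let P be positives, N episodes tested, m missed episodes and q their positivity. The observed rate is (P − mq)/(N − m), which is below P/N only if q > P/N. If missed illnesses are less often positive, the rate rises. If the outcome is any infection in the household, a missed grandparent episode matters only when no other member already counts.

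**The case against.** The best reply is that the plan has more routes to the elderly than the LINE group.

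- A reader might infer that all testing of the elderly depends on their own reported symptoms. It does not: household members are screened after another member's lower respiratory illness, including the baby's, and the family questionnaire then asks about current or recent symptoms.
- A reader might also infer that surveillance runs exclusively through the parent. The text says the family replies, the interviews at 2, 4 and 8 weeks act on any member's report, and setting up a group with a parent does not exclude other relatives. If the weekly household visits in the Infected model section take place, much of the concern falls away.
- Proxy reporting is not confined to grandparents. A parent outside the LINE group, and young siblings, are reported by proxy in both family types. The contrast between grandparents and everyone else is therefore less sharp than the 90% assumption suggests.
- The unreproduced Google questionnaire may already list members.

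These points stand and limit the claim. They do not remove it. Screening follows lower respiratory illness only, and only in the same household. The interviews start after a first episode and so cannot detect one. The weekly visits appear in one sentence that conflicts with the procedures. No section says how a grandparent's mild illness becomes known.

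**Conclusion.** The concern holds as a design risk. Routine surveillance names the parent or guardian, asks at household level, and specifies no route for grandparents, who are in one comparison group only. Their milder illnesses may be captured less completely, which could bias the family-type comparison and the index/secondary ordering.

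It would go too far to say that grandparents are under-counted, or that the extended-family rate is biased towards or below the nuclear rate by a known amount. Under-capture is an inference. The 4-18% figure, and the fall in power to between 80% and 35%, rest wholly on assumed capture rates and shares and on a per-person incidence reading. With the isolation-rate denominator unstated, even the sign is open. The case for change is that the gap is plain in the text, cannot be repaired at analysis, and is cheap to close.

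**What to change.** In Patient recruitment and management and in LINE management:

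1. Replace the household-level weekly check with one yes/no symptom item per enrolled member, with absence of symptoms recorded explicitly.
2. Have it answered by each consenting adult in the LINE group, or by one named adult who asks each grandparent directly.
3. Use the same member list in the monthly call.
4. Report response rates by role (parent, child, grandparent) and by family type, so that any differential capture can be seen.
5. Reconcile the weekly household visits in the Infected model section with the symptom-triggered visits in the procedural sections.

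**Cost.** This uses the existing LINE group, questionnaire and call, with no new scheduled visits or procedures. Weekly replies become slightly longer. If reporting improves, somewhat more episodes will need a visit and swab under the existing rule, so the specimen workload may rise.
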